## 6. Patient screening

### 6.1 Patient screening

All patients who are admitted with new stroke symptoms on awakening should be screened for inclusion into the trial. Patients will be evaluated for vital signs, physical examination, neurological status (NIHSS), ECG and CT with CT angiography (section 6.2). Routine blood tests will include blood glucose and prothrombin time/INR\*, aPTT\*, TT and/or eucarin clotting time if it is suspected the patient is taking direct thrombin inhibitors or direct factor Xa inhibitors.

\*Although it is desirable to know the results of these tests before giving intravenous tenecteplase, fibrinolytic therapy should not be delayed while awaiting the results unless (1) there is clinical suspicion of a bleeding abnormality or thrombocytopenia, (2) the patient has received heparin or warfarin within 48 hours, or (3) the patient has received other anticoagulants/direct thrombin inhibitors or direct factor Xa inhibitors.

## **6.2 Non-contrast CT and CT angiography for patient screening before randomisation**

All patients should be screened with non-contrast CT, and CT angiography should be performed, if possible. Findings on non-contrast CT shall only be used to exclude patients who are unlikely to benefit from treatment (See Exclusion criteria in Section 5). If other, advanced imaging examinations are used (see sections 6.3 and 6.4, below), findings on such examinations shall not influence the decision to include the patient, unless the results of such imaging show that the patient should or should not receive thrombolytic treatment, in the opinion of the investigator.

## **6.3 CT perfusion at selected centres before randomisation (substudy)**

Some centres routinely use CT perfusion in patients with wake-up stroke, and these centres will be invited to participate in a substudy of CT perfusion. All CT scans taken in the trial will be sent to the Trial Co-ordinating Centre for central, blinded analysis.

## **6.4 Routine use of MRI before randomisation**

Some centres routinely use MRI perfusion or MRI DWI/FLAIR in patients with wake-up stroke. These examinations are not part of the trial, but MRI examinations done of patients included into the trial shall be sent to the Trial Coordinating Centre for central, blinded analysis. Extra brain scanning (CT perfusion or MRI) must not delay treatment, and we will discourage extra scanning if randomisation is delayed more than 20 minutes.

# **7. Patient inclusion**

## **7.1 Patient information and consent/assent**

Written, informed consent will be sought from all eligible patients. If the patient can consent but cannot sign, non-written consent from the patient (witnessed by non-participating health care personnel) can be accepted. If the patient is unable to consent, his/her legal representative and/or next of kin can consent on the patient's behalf depending on national legislation. The regulations governing these procedures may vary from jurisdiction to jurisdiction. The procedures for obtaining consent will therefore have to be approved for each jurisdiction, and will be described in separate standard operating procedures. It is noted that legal restrictions in some EU Member States prevent performing any trial-specific interventions (e.g. treatment or trial-specific diagnostic procedures without obtaining prior informed consent).

If a patient was unable to give consent at trial entry, but regains capacity to receive information and give consent, he/she will be given information as soon as possible and asked whether he/she is willing to continue his/her participation in the trial. The patient and his/her legal representative will be informed of the right to withdraw from the trial and object to the use of his/her data.

## **7.2 Randomisation procedure and recording of baseline characteristics**

Patients will be randomly allocated to tenecteplase or control in a 1:1 ratio. Randomisation will be performed by central computer over the Internet. The investigators will record patient details via a secure web interface before randomisation takes place. Investigators may also contact the Trial Coordinating Centre via the 24-hours help-line.

The randomisation procedure will include a standard minimisation algorithm which will ensure that the treatment groups are balanced for key prognostic factors, such as sex, age, NIHSS score, stroke type (OCSF subgroup), delay to thrombolytic treatment, and use of antiplatelet drugs within the past 24 hours. To avoid predictable alternation of treatment allocation, and thus potential loss of allocation concealment, patients will be allocated with a probability of 0.80 to the

treatment group that would minimise the difference between the groups on the key prognostic factors.

## **8. Trial treatment**

Patients will be randomly allocated to open-label tenecteplase plus best standard care or to best standard care alone.

### **8.1 Open-label tenecteplase plus best standard care**

The total dose of tenecteplase is 0.25 mg per kg of body weight (maximum 25 mg). The dose shall be given as an intravenous bolus. Patients will be on bed rest in accordance with local routine following administration of tenecteplase.

After infusion, vital signs, neurological signs and blood pressure will be monitored every 15 minutes for two hours, then every 30 minutes for 6 hours, then 60 minutes until 24 hours from the start of treatment. Blood pressure should be maintained at or below 180/105 mmHg during the first 24 hours. Placement of intra-arterial catheters, indwelling bladder catheters, and nasogastric tubes shall be avoided for 24 hours if the patient can be safely managed without them. Venipunctures should be performed and monitored carefully.

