### **8.2 Best standard care alone**

Patients randomised to control shall not be given tenecteplase or any other thrombolytic agent.

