### **8.3 Best standard care and other treatments**

Both arms will receive best standard care, including intra-arterial interventions for proximal cerebral artery occlusion. If the patient is given tenecteplase, then aspirin or other antiplatelet or anticoagulant drugs shall not be given until 24 hours after termination of infusion and after the control CT brain scan. If the patient was allocated to control, he/she will receive aspirin 300 mg as a loading dose as soon as possible after randomisation. After the first 24 hours the recommended daily dose of aspirin is 75 mg once daily in both the tenecteplase group and the control group. Best standard care during the first week also includes treatments to maintain normal homeostasis (temperature, blood glucose, hydration, nutrition), as well as lipid lowering and blood pressure lowering drugs, in accordance with clinical guidelines. Clinical examinations, including additional CT scans will be performed as clinically indicated.

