### **8.4 Management of serious adverse events related to study treatment**

The management of serious adverse events that can be related to treatment with tenecteplase will be guided by specific, detailed standard operating procedures. All patients with neurological deterioration will undergo emergency head CT. In case of a major bleeding (e.g. intracranial haemorrhage), antifibrinolytic agents or transfusion of cryoprecipitate, fresh frozen plasma or platelets may be indicated and should be considered. The investigator should institute any supplementary investigations of serious adverse events based on their clinical judgement of the likely causative factors. This may include seeking further opinion from a specialist in the field of the adverse event.

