### 9.1 Visits and examinations during stay in hospital

Clinical visits: These will be performed on day 1 (at baseline) and day 7 (or on the day of discharge, whichever occurs first). NIHSS will be performed at both times. ECG will be performed on day 1. Clinical events will be recorded on day 7 (or on the day of discharge). Outcome assessors will be blinded to the assigned treatment group.

Routine blood analysis will be performed on day 1 (at baseline) and day 7 (or on the day of discharge, whichever occurs first). Tests on day 1 will include: haemoglobin, creatinine, blood glucose, platelets, prothrombin time/INR, aPTT, TT and/or eucarin clotting time if it is suspected that the patient is taking direct thrombin inhibitors or direct factor Xa inhibitors.

Non-contrast CT and CT angiography (if possible): All patients will undergo non-contrast CT and CT angiography (if possible) before randomisation, and again at 24±6 hours after randomisation. CT angiography at 24±6 hours will only be performed in patients with a positive finding on CT angiography before randomisation.

CT perfusion will be performed at selected centres.

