### 10.2 Secondary effect variables

#### *Clinical events:*

- Any intracranial haemorrhage during follow-up
- Symptomatic intracranial haemorrhage by SITS-MOST definition
- Symptomatic intracranial haemorrhage by IST-3 definition
- Parenchymal haemorrhage type 2Stroke progression during follow-up
- Recurrent ischaemic stroke during follow-up
- Major extra cranial bleeding
- Death from all cause during follow-up

Clinical events are defined in the Appendix.

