### 16.2.6 Neurological deterioration due to index stroke

The definition is an increase of  $\geq 2$  points in one or more of the NIHSS (irrespective of improvement in any of the other NIHSS sub-scores). When diagnosing neurological deterioration due to index stroke, systemic reasons for deterioration, such as drug-induced hypotension, drug-induced drowsiness, and intercurrent disease should be excluded. No significant haemorrhage should be found on post randomization CT or MR scan.

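### Neurological checks in the first 24 hours are scheduled only for the tenecteplase arm, so early stroke progression may be detected more often there than on control

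*Protocol*

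**What the plan says.** Protocol section 8.1, on the tenecteplase arm, states that after dosing "vital signs, neurological signs and blood pressure will be monitored every 15 minutes for two hours, then every 30 minutes for 6 hours"; the interval is hourly after that, up to the end of the first day. Section 8.2, on control, is one sentence: "Patients randomised to control shall not be given tenecteplase or any other thrombolytic agent". It mentions no observations. Section 8.3, which covers both arms, adds only that "Clinical examinations, including additional CT scans will be performed as clinically indicated". The older version, in the combined document, has the same pattern in sections 8.1.1 to 8.1.3.

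Section 10.2 lists "Stroke progression during follow-up" among the clinical events. The appendix has no entry under that name. The matching definition is 16.2.6: an NIHSS rise of at least 2 points, counted "irrespective of improvement in any of the other NIHSS sub-scores". It sets no examination times and no minimum duration. Under 16.2.3, deterioration after 72 hours, once other causes are excluded, is a recurrent stroke.

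Section 9.1 schedules clinical visits at baseline and at day 7 or discharge; "NIHSS will be performed at both times". Clinical events are recorded at the later visit. Section 10.2 also names the NIHSS at 24 hours as an outcome, but neither Table 2 nor section 9.1 schedules it. Section 8.4 states: "All patients with neurological deterioration will undergo emergency head CT".

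**The concern.** A worsening that appears and resolves on day 1 leaves no trace at the scheduled NIHSS examinations. It becomes an event only if someone at the bedside notices it, and for that the plan gives a schedule in one arm only. The trial is open-label, so ward staff know the allocation. The definition accepts a short-lived change on part of the scale, so the recorded rate depends on how often patients are examined.

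An apparent excess of progression on tenecteplase could then come partly from closer observation, or a real reduction could be hidden. A noticed deterioration also leads to a CT, which can bring a haemorrhage to light. Blinded outcome assessors (9.1) and blinded adjudication (12.6) judge what was recorded; neither restores what was missed.

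**Working it through.** **1. The plan's own figure.** The documents give no rate, power or sample size for progression or haemorrhage. The only design figure is N = 600 for the ordinal mRS analysis (11.1: odds ratio 1.50, 80% power, two-sided 5%, control distribution 15, 27, 23, 17, 13, 5%). With the Whitehead formula,

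N = 12(1.960 + 0.842)² / [(ln 1.5)² (1 − Σp̄³)],

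where p̄ is the mean of the control distribution and the distribution shifted by an odds ratio of 1.5, the result is 600.8. The figure reproduces. No in-hospital event enters it, and the mRS is collected centrally and blinded at 90 days (9.2), so this point touches neither.

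**2. Scheduled checks in 24 hours (section 8.1).** 120/15 = 8; 360/30 = 12; the remaining 24 − 8 = 16 hours give 16. Total 8 + 12 + 16 = 36 on tenecteplase. For control no number is stated. The section speaks of neurological signs; it does not say that the NIHSS is scored each time.

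**3. Exposure of each outcome.**

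| Outcome | Limit in the plan | Ascertainment common to both arms | Exposure |
|---|---|---|---|
| Stroke progression (10.2, 16.2.6) | None in 16.2.6; 16.2.3 takes over after 72 h | NIHSS at baseline and day 7/discharge only | Main |
| Symptomatic haemorrhage, IST-3 (16.2.4) | 7 days; symptoms such as headache or nausea count | CT at 24±6 h for the imaging part | Lesser |
| Any intracranial haemorrhage (10.2) | None; unscheduled scans count | CT at 24±6 h | Lesser |
| Symptomatic haemorrhage, SITS-MOST (16.2.4) | 22–36 h scan; type 2 haematoma plus a rise of 4 points, or haemorrhage leading to death | CT at 24±6 h | Largely protected |
| Type 2 parenchymal haemorrhage | Imaging definition | CT at 24±6 h, read centrally and blinded (6.3) | Largely protected |

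**4. Illustration for progression.** All rates here are assumptions. Let the true risk p be equal in both arms, let every event be detected on tenecteplase, and let a fraction d be detected on control. Then

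observed control risk q = p·d; apparent OR = [p/(1 − p)] / [q/(1 − q)]; extra recorded events per 300 = 300(p − q).

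The chance of a significant result is from a two-sided 5% normal-approximation test of two proportions with 300 per arm.

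| p | d | q | Apparent OR | Extra events per 300 | Chance of p < 0.05 |
|---|---|---|---|---|---|
| 10% | 90% | 9% | 1.12 | 3 | 7% |
| 10% | 80% | 8% | 1.28 | 6 | 14% |
| 10% | 70% | 7% | 1.48 | 9 | 26% |

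For example, (0.10/0.90)/(0.08/0.92) = 0.1111/0.0870 = 1.28. Over p from 5% to 20% and d from 70% to 95%, the apparent odds ratio runs from 1.06 to 1.54, the extra events from about 1 to 18 per 300, and the false-positive chance from 5% to 50%.

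**The case against.** Silence about control is not evidence of fewer checks. Control patients receive best standard care, which may include frequent observation on the same ward; the plan just does not state it. A reader might infer 36 checks against none, but the documents support only 36 against an unspecified number. The sentence on examinations in section 8.3 applies to both arms and is not a control-arm rule. The 36 checks are also not shown to be NIHSS assessments, which 16.2.6 requires. That section excludes systemic causes and significant haemorrhage, and the 72-hour rule limits progression in time. All of this stands, and it is why the size cannot be stated.

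A reader might also infer that symptomatic haemorrhage is an any-time event, so that its rates cannot be compared. The definitions do not allow that: IST-3 stops at seven days and SITS-MOST is tied to the 22–36 h scan. Both arms have a CT at 24±6 h with central blinded reading, and closer observation cannot create a type 2 haematoma. Nor do the documents show that tenecteplase patients will have more unscheduled scans; that is only possible.

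Section 11.2 refers to a detailed statistical analysis plan whose text is not in the documents supplied; it may already treat these events. None of this gives progression a common examination schedule in the protocol.

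**Conclusion.** The plan carries a risk of differential detection of stroke progression, of unknown size and mainly against tenecteplase. It rests on three features of the text: a first-day check schedule written for one arm, an event definition without common examination times or persistence, and open-label care. IST-3 symptomatic haemorrhage and any intracranial haemorrhage share the risk to a lesser degree; SITS-MOST and type 2 parenchymal haemorrhage largely escape it.

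To call the arms' rates not comparable would go too far, because control monitoring is unstated rather than absent. The odds ratios above show what assumed detection gaps would do and estimate nothing about this trial. If sites observe both arms alike, the bias vanishes, but the protocol does not say that they do. The point concerns secondary outcomes and should be addressed; the primary mRS analysis and N = 600 stand.

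**What to change.** 1. Base the between-arm comparison of progression on NIHSS examinations at the same times in both arms: baseline against 24 hours, and baseline against day 7 or discharge. State in advance how deaths before an examination are counted. Keep progression seen at other times as a listing by arm. Enter the 24-hour NIHSS, already named in section 10.2, in Table 2 and section 9.1.
2. Add a sensitivity analysis of any haemorrhage and type 2 parenchymal haemorrhage restricted to the scheduled 24±6 h CT, read centrally and blinded. Report by arm the number of unscheduled scans and the haemorrhages found only on them.
3. Reconcile sections 8.1, 8.2 and 8.3 on which observations apply to which arm. What the observations should be is for the trial team; this review proposes none.

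Cost: definition and analysis-plan wording plus one entry in the visit schedule, with no change to N or the primary analysis. Transient deteriorations that resolve before a scheduled examination leave the comparative outcome and appear only in the listing. Day 7 or discharge is a common nominal time only, because stays differ, so the 24-hour comparison is the cleaner one.

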### **8.2 Best standard care alone**

Patients randomised to control shall not be given tenecteplase or any other thrombolytic agent.

### **8.3 Best standard care and other treatments**

Both arms will receive best standard care, including intra-arterial interventions for proximal cerebral artery occlusion. If the patient is given tenecteplase, then aspirin or other antiplatelet or anticoagulant drugs shall not be given until 24 hours after termination of infusion and after the control CT brain scan. If the patient was allocated to control, he/she will receive aspirin 300 mg as a loading dose as soon as possible after randomisation. After the first 24 hours the recommended daily dose of aspirin is 75 mg once daily in both the tenecteplase group and the control group. Best standard care during the first week also includes treatments to maintain normal homeostasis (temperature, blood glucose, hydration, nutrition), as well as lipid lowering and blood pressure lowering drugs, in accordance with clinical guidelines. Clinical examinations, including additional CT scans will be performed as clinically indicated.

### **8.4 Management of serious adverse events related to study treatment**

The management of serious adverse events that can be related to treatment with tenecteplase will be guided by specific, detailed standard operating procedures. All patients with neurological deterioration will undergo emergency head CT. In case of a major bleeding (e.g. intracranial haemorrhage), antifibrinolytic agents or transfusion of cryoprecipitate, fresh frozen plasma or platelets may be indicated and should be considered. The investigator should institute any supplementary investigations of serious adverse events based on their clinical judgement of the likely causative factors. This may include seeking further opinion from a specialist in the field of the adverse event.

## 9. Visits and examinations from trial entry till end of follow-up

The duration of the follow-up period is 3 months. During this period, all patients should be treated according to standard clinical guidelines, at the discretion of the clinician. Table 2 gives an overview of all visits and examinations in the trial.

**Table 2. Scheme for visits and examinations**

	Days			Months
	1	2	7	3
Clinical visit	x		x	
Routine blood analysis	x		x	
CT + CT angiography (if possible) before randomisation	x			
CT perfusion, at selected centres	(x)			
CT + CT angiography (if possible) 24±6 hrs after randomisation		x		
Centralised follow-up				x

Day 1 is the day of entry into the trial. \*Day 7 or day of discharge, whichever occurs first.

### 9.1 Visits and examinations during stay in hospital

Clinical visits: These will be performed on day 1 (at baseline) and day 7 (or on the day of discharge, whichever occurs first). NIHSS will be performed at both times. ECG will be performed on day 1. Clinical events will be recorded on day 7 (or on the day of discharge). Outcome assessors will be blinded to the assigned treatment group.

Routine blood analysis will be performed on day 1 (at baseline) and day 7 (or on the day of discharge, whichever occurs first). Tests on day 1 will include: haemoglobin, creatinine, blood glucose, platelets, prothrombin time/INR, aPTT, TT and/or eucarin clotting time if it is suspected that the patient is taking direct thrombin inhibitors or direct factor Xa inhibitors.

Non-contrast CT and CT angiography (if possible): All patients will undergo non-contrast CT and CT angiography (if possible) before randomisation, and again at 24±6 hours after randomisation. CT angiography at 24±6 hours will only be performed in patients with a positive finding on CT angiography before randomisation.

CT perfusion will be performed at selected centres.

### 9.2 Centralised follow-up via telephone or mail at 3 months (90 ±7 days)

At 90±7 days, the Trial Coordinating Centre will contact patients (or their carers) via telephone (alternatively, via postal mail), blinded to the treatment that the patients received. We may also need to contact the patients' general practitioners and local hospitals to get information from the patients' medical records. We will record information about clinical events, functional status (mRS), activities of daily living (BI), health-related quality of life (EuroQol), and cognitive status (MMSE, TICS-M).

### 9.3 Long-term follow-up by record linkage with central registries

We will collect data up to three years from trial entry, by using record linkage with data from central registries such as national patient registries and the cause-of-death registries in the participating countries.

## 10. Effect variables

### 10.1 Primary effect variable

Functional outcome (defined by the mRS) at 3 months

### 10.2 Secondary effect variables

#### *Clinical events:*

- Any intracranial haemorrhage during follow-up
- Symptomatic intracranial haemorrhage by SITS-MOST definition
- Symptomatic intracranial haemorrhage by IST-3 definition
- Parenchymal haemorrhage type 2Stroke progression during follow-up
- Recurrent ischaemic stroke during follow-up
- Major extra cranial bleeding
- Death from all cause during follow-up

Clinical events are defined in the Appendix.

#### *Clinical outcomes:*

- Favourable functional outcome at 3 months: mRS 0-1
- Good functional outcome at 3 months: mRS 0-2
- NIHSS score at 24 hours and day 7
- Change in NIHSS score from baseline to 24 hours and day 7
- Barthel Index score at 3 months
- EuroQol score at 3 months
- MMSE score at 3 months

